1.3.2 Clinical pharmacokinetic and safety

PK data available from clinical trials until now indicate that afatinib was moderately fast absorbed after oral administration, with median t_{max} values mainly between 2 and 5 hours. For afatinib there was no deviation from dose-proportionality detectable. However, moderate to high inter- and intra-individual differences in plasma concentrations were seen. Afatinib was highly distributed out of the blood and had a moderate to high clearance. The gMean terminal half-life was mainly in the range of 13-57 h. Steady state was reached no later than 8 days after the first administration. The major route of elimination of afatinib was via the faeces. After food intake, a decreased systemic exposure was observed compared to administration of afatinib under fasted conditions. Typically, an accumulation ratio based on AUC values between 1.8 and 4.0 has been observed. At doses of 40 mg and above individual $C_{max,ss}$ and $AUC_{t,ss}$ values were mainly in the same range as those found to demonstrate anti-tumor activity in nude mouse tumor xenograft models.

Adverse events observed with afatinib are consistent with those reported for other EGFR- and dual EGFR/HER2-inhibitors. These include predominantly gastrointestinal (GI) and dermatological adverse events which are dose-dependent. Diarrhea, including severe diarrhea, has been reported during treatment with afatinib. Diarrhea may result in dehydration with or without renal impairment, which in rare cases has resulted in fatal outcomes. Diarrhea usually occurred within the first 2 weeks of treatment. Patients of low body weight, females, and patients with low

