In trial 1200.5 Afatinib PK parameters were within the ranges observed in afatinib monotherapy studies (PK meta-analysis [U10-1153]), suggesting that continuous dosing in combination with 2.5 mg letrozole had no major influence on afatinib PK. Mean PK parameters for letrozole showed no trend to higher or lower values in conjunction with afatinib dosing. The observed letrozole PK parameters were in the ranges reported in the literature ([R10-4018] and [R10-4019]), suggesting that afatinib did not have a relevant effect on letrozole PK. Therefore, there was no indication of a DDI between letrozole and afatinib and vice versa (when compared with literature or historical data). Based on this data it is not planned to further evaluate PK interactions in this combination.

A detailed section on the management of adverse events, among which diarrhea and rash, has been incorporated in the protocol with some proactive precautions to avoid occurrence or aggravation of these specific adverse events at a very early point.

Protocol amendment 4.0 was released on 09 May 2016 and its main change was the enrollment closure due to insufficient efficacy data to pursue development of afatinib in breast cancer and low recruitment in the trial. As of the date of release of this new protocol amendment, there are 6 patients still on treatment in the trial and among those, only 2 patients are treated with the combination of letrozole and afatinib (Arm B). Due to the limited number of patients still on treatment, and especially in Arm B, TRIO and BI agreed to release this amendment to discontinue the trial, allowing patients receiving afatinib to continue with this treatment outside of the TRIO-020 trial.

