5.3.3 Protocol treatment discontinuation

By default, patients are treated until progressive disease as per RECIST 1.1.

Please refer to section 3-Trial Design (IN ADDITION) regarding the decision to discontinue the patients from the trial at the latest on 30 November 2018 and the conditions of this discontinuation.

The investigator will also discontinue the treatment if any of the following conditions is met:

- ✓ Intercurrent illness or change in patient's condition that warrants trial treatment discontinuation or unacceptable toxicity, such as interstitial lung disease, rash grade 4, hepatic injury, left ventricular systolic dysfunction grade ≥ 3 , ulcerative keratitis (see section 5.4)
- ✓ Any event which would warrant afatinib to be modified by > 1 dose reduction or afatinib to be held for > 14 days (see section 5.4.1)
- ✓ Need for additional local and/or systemic non-protocol anticancer therapy (see section 5.5.4)
- ✓ Patient's decision to withdraw
- ✓ Lost to follow up
- ✓ Death
- ✓ Pregnancy (see section 7.4.2)
- ✓ Investigator's decision
- ✓ Discontinuation of the trial by the sponsor

Refer to section 6.3 for the list of assessments to be performed at the end of treatment.

If letrozole needs to be discontinued for any reason then afatinib must also be discontinued and patient must be discontinued from the trial except if patient is deriving obvious clinical benefit from continuing treatment with afatinib alone. **Please refer to section 5.4.1 for the protocol definition of obvious clinical benefit.**

In this case, Medical Monitor/TRIO Medical Lead/Trial Chair should be contacted by the site prior to continuing with afatinib.

If afatinib needs to be discontinued for any reason, letrozole should be discontinued within the frame of the trial and the patient must be discontinued from the trial.

Last trial dose of letrozole as trial medication will be defined as last letrozole intake prior to End of Study Visit.

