8.4 Safety Endpoints

Adverse Events - The latest version of the Medical Dictionary for Regulatory Activities (MedDRA) will be used to code all adverse events to a preferred term and system organ class. Adverse events will be graded using the Common Terminology Criteria for Adverse Events (NCI CTCAE v4.0). Patient's incidence of adverse events will be tabulated by system organ class, preferred term and toxicity grade by treatment arm. Adverse events leading to death or drug discontinuation, drug related and serious adverse events will also be summarized by treatment arm.

Detailed listings for all adverse events will also be provided.

Laboratory parameters - Laboratory parameters, graded according to the NCI CTCAE v4.0, will be summarized at baseline, along visits and at the end of trial treatment by treatment arm. Tables of shifts in toxicity will also be provided.

Other Safety Data – Vital signs (weight and blood pressure), ECOG and LVEF will be summarized at baseline, along visits and at the end of trial treatment by treatment arm. Tables of shifts in toxicity will also be provided when applicable.

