### **Treatment Emergent Adverse Event (TEAE)**

An AE will be considered treatment emergent if:

Its onset date occurred any time on or after the administration of the first dose of any study treatment up to 30 days after the last dose of study treatment (or up to any time if serious AE related to study treatment).

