### **10.6.1 Adverse Events**

The Medical Dictionary for Regulatory Activities (MedDRA version 16.0 or later) will be used to code all adverse events to a system organ class and a preferred term.

Subject incidence of Treatment Emergent Adverse Events will be tabulated by system organ class, preferred term and toxicity grade for all adverse event, serious, treatment-related, and serious treatment-related adverse events. Each of these outputs will include tabulation for each system organ class and preferred term as reported by the investigator based on Common Terminology Criteria for Adverse Events (CTCAE), version 4.0.

Summary tables will be provided separately for Treatment Emergent Adverse Events leading to investigational product discontinuation and Treatment Emergent Adverse Events leading to study withdrawal.

All AEs leading to deaths will be summarized (not only TEAEs). An AE will be considered as leading to death if it has a grade 5.

Detailed listings for all adverse events and listings and/or narratives will be provided for serious and significant adverse events, deaths, and treatment discontinued due to adverse events. A flag will be used to identify which adverse events are considered as treatment emergent or not.

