**BIostatistics**  
**Statistical Analysis Plan**  
**TRIO-020**  
**STAT-020-SAP**

Title	Population	Description
		Status at Registration, Prior Surgery for Breast cancer and Prior Anti-Tumor Therapy.
Study Drug Exposure	Safety	Tabulates the Number of Cycles, the Duration of Treatment, the Cumulative dose, the Relative dose intensity, Reductions.  The number of subjects with dose interruptions/discontinuation or reduction will also be summarized.
Progression-Free Survival	ITT	Summary of PFS results including treatment comparison results.
Progression-Free Survival	ITT	Summary of PFS results including treatment comparison results (sensitivity analysis).
Overall Survival	ITT	Summary of OS results including treatment comparison results.
Objective Response Rate	ITT	Summary of ORR results including treatment comparison results.
Time to Progression	ITT	Summary of TTP results including treatment comparison results.
TEAEs Overview	Safety	Tabulates the number of TEAEs, serious TEAEs, Grade 3-4 TEAEs, Treatment Related TEAEs, Serious and Treatment Related TEAEs, Fatal TEAEs.
Treatment Emergent Adverse Events (TEAEs)	Safety	Summary by system organ class and preferred term for each treatment group.

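### Treatment-emergent adverse events are planned only as crude incidence over a window that follows time on treatment; descriptive patient-time and fixed early-window tables should be added

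*SAP*

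**What the plan says.** SAP 10.6.1: "Subject incidence of Treatment Emergent Adverse Events will be tabulated by system organ class, preferred term and toxicity grade". Protocol 8.4 sets the same measure: "incidence of adverse events will be tabulated by system organ class, preferred term and toxicity grade by treatment arm". In SAP 11.1 there is a TEAE overview, which tabulates numbers of TEAEs, and 17 further TEAE tables, each described as "Summary by system organ class and preferred term for each treatment group". They are split by grade, seriousness, relatedness, discontinuation or fatal outcome. None has a patient-time denominator, a time to onset or a common window.

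SAP 4.2 starts the TEAE window at first dose and runs it "up to 30 days after the last dose of study treatment". Serious events related to treatment count without a time limit, and SAP 10.6.1 summarises fatal events whether or not they are treatment emergent.

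Three provisions bear on time on treatment:
- Protocol 5.3.3 treats patients to RECIST progression by default, and SAP 5.2 plans on median PFS of 9 months (control) and 14 months (experimental).
- Protocol 5.3.3 also states: "If afatinib needs to be discontinued for any reason, letrozole should be discontinued within the frame of the trial". The patient then leaves the trial.
- Protocol section 3 takes the remaining Arm A patients off trial when the Arm B patients stop, and everyone by 30 November 2018.

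Duration of treatment is summarised by arm in a separate table (SAP 10.4). Protocol 2.1.2 now limits reporting to description per arm, without statistical comparison.

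**The concern.** The proportion of patients with an event depends on how often the event occurs and on how long patients are observed. If the two windows differ in length, side-by-side crude incidences can show a difference where the underlying rate is the same, or conceal one where it is not. A table of treatment duration tells the reader that exposure differed, but a per-term incidence cannot be adjusted from it.

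This matters more now than when the SAP was written. Protocol section 8 now specifies only baseline, treatment and safety summaries, so the per-arm safety description is the main output left. The provisions above pull in opposite directions. Longer PFS would lengthen the Arm B window, leaving when afatinib stops would shorten it, and the closure rules can cut Arm A as well.

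**Working it through.** **Planning medians.** They reproduce the SAP's own event count. With hazard ratio 9/14 = 0.643, two-sided alpha 10% and power 80%, Schoenfeld's formula gives 4 × (1.645 + 0.842)² / (ln 0.643)² = 126.7, so 127 events, as in SAP 5.3.

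**Inputs from the documents.** Medians 9 and 14 months; 18-month accrual and about 42 months in total (SAP 5.2); 30-day tail (SAP 4.2), D = 30/30.44 = 0.986 months.

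**Assumptions.** Time on treatment is exponential with the PFS medians and independent of the event. The event hazard h is constant and equal in both arms (1%, 2% or 5% per month). Medians of 5 and 6 months stand for a shorter Arm B exposure. None of these is an observed figure.

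**Formula.** Crude incidence = 1 − exp(−hD) × μ/(μ + h), with μ = ln 2 / median.

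At h = 0.02, exp(−hD) = 0.9805:
- Median 9: μ = 0.0770; 1 − 0.9805 × 0.0770/0.0970 = 22.2%.
- Median 14: μ = 0.0495; 1 − 0.9805 × 0.0495/0.0695 = 30.2%.

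The mean windows, 1/μ + D, are 14.0 and 21.2 months.

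**Cap.** A patient has c months available, with c uniform from 42 − 18 = 24 to 42. Replace μ/(μ + h) by μ/(μ + h) × (1 − exp(−(μ + h)c)) + exp(−(μ + h)c) and average over c. At h = 0.02 this gives 21.2% and 27.1%.

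| h per month | median 9 | median 14 | median 5 | gap 14 − 9, uncapped | gap 14 − 9, capped |
|---|---|---|---|---|---|
| 1% | 12.4% | 17.6% | 7.6% | 5.3 points | 3.5 points |
| 2% | 22.2% | 30.2% | 14.3% | 8.0 points | 5.9 points |
| 5% | 42.3% | 52.6% | 30.0% | 10.4 points | 9.0 points |

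Gaps are taken from unrounded values.

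**Concealment.** With medians 9 (Arm A) and 6 (Arm B) and a true 1.5-fold hazard in Arm B (3% against 2%), crude incidence is 22.2% against 22.9%.

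**Common early window.** For W = 84 days = 2.76 months, observation ends at the earlier of W and last dose plus 30 days. Incidence = 1 − [exp(−hD) × μ/(μ + h) × (1 − exp(−(μ + h)(W − D))) + exp(−μ(W − D) − hW)]. At h = 0.02 this is 5.1%, 5.2% and 5.0% for medians 9, 14 and 5, so the artefact nearly vanishes.

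**Patient-time.** With time censored at first event, expected time at risk is incidence/h. At h = 0.02 that is 11.1 months (median 9) and 15.1 months (median 14), and 22.2/11.1 and 30.2/15.1 both return 2.0 first events per 100 patient-months.

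**The case against.** The case against is substantial.

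- **Unequal windows are not established.** The window rule is the same in both arms, the 9 and 14 months are planning hypotheses, and no exposure by arm is reported. A reader might infer that exposure differs by design, or that the tables will overstate Arm B toxicity. The documents support neither. Protocol 1.4 notes that "there are 6 patients still on treatment in the trial and among those, only 2 patients are treated with the combination", but without numbers randomised per arm this does not show which arm was treated longer.
- **The Arm B stopping rule is not absolute.** Protocol 5.4.1 runs Arm B adverse event monitoring to last letrozole where afatinib stopped earlier, which has to be read together with 5.3.3. It also leaves room for case-by-case decisions when a patient is deriving benefit. Arm A has its own truncation.
- **Not every table is confined to the window.** Related serious events and fatal events are not.
- **Early toxicity is largely safe.** Protocol 1.3.2 says "Diarrhea usually occurred within the first 2 weeks of treatment" and that half of rash/acne cases begin within 4 weeks. The 30-day tail keeps treated patients under observation for at least about a month, barring death or withdrawal.
- **Part of the information is already planned.** Duration of treatment is tabulated by arm, events leading to drug discontinuation have their own tables and listing, and onset dates and exposure are listed per subject.
- **The reporting is descriptive.** Crude incidence is what the protocol specifies, and nothing in it is contradictory.

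All of this limits the size and certainty of the point. It does not answer the case of later or steadily accruing events, where a separate duration table cannot correct a per-term incidence.

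**Conclusion.** The point holds as a cheap improvement to the safety description; the planned tables are not in error. If treatment durations followed the SAP's medians, an event with an equal 2% monthly hazard would show a crude excess in Arm B of 8.0 points uncapped, or about 6 points within the planned accrual and duration. Across hazards of 1% to 5% the range is 5.3 to 10.4 points uncapped and 3.5 to 9.0 capped. With a shorter Arm B exposure the sign reverses: at a median of 5 months against 9, 14.3% against 22.2%.

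These figures rest on assumed constant hazards and on exponential treatment times independent of the event. They show what the tables could do, not what they will show. Early diarrhoea and early rash are largely outside the concern.

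**What to change.** Keep all crude tables. Add to SAP 10.6.1 and 11.1, as description by arm with no test:

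1. In the TEAE overview and for the main preferred terms: patient-months at risk, and subjects with a first event per 100 patient-months at risk. Time is censored at the first event of that type, and both events and time are limited to first dose through 30 days after last dose. The open-ended extension for related serious events stays out of the rate.
2. TEAE incidence in a common early window from first dose, by preferred term and worst grade. The first 84 days is a convenient choice (three 28-day cycles, matching the 12-week assessment interval); it is a convention and should be stated as one.

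The cost is two more tables from first-dose, last-dose and onset dates already collected, with no change to sample size or conduct. The patient-time rate assumes a constant hazard, so a footnote should direct readers to it for late events and to the fixed-window table for early ones.

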### **10.6.2 Performance Status, Physical Exams, Vital Signs, and Laboratory Evaluations**

Summary of ECOG Performance Status results at each scheduled time point (including baseline) and the change from baseline will be presented. A shift table will be provided as well from baseline status to the worst status of post-baseline time points.

Vital sign measurements (only systolic and diastolic blood pressure) will be summarized at each visit (maximum value on day of dosing) and over the study, using descriptive statistics. In addition, shifts from baseline will be tabulated, by cycle (maximum value on

day of dosing) and over the study, with systolic blood pressure categorized as <140, 140-160, >160 mmHg, and diastolic blood pressure as <90, 90-100, >100 mmHg.

Body weight and change from baseline will be summarized by visit.

LVEF and change from baseline will be summarized by visit.

Laboratory parameters for Hematology and Blood chemistry results at each scheduled time point (including baseline) and the change from baseline will be presented. A shift table will be provided as well from baseline status to the worst status of post-baseline time points.

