Blood chemistry: AST, ALT, Alkaline Phosphatase, Total Bilirubin and Creatinine.

⁷ LVEF will be assessed every 12 weeks during treatment phase and when clinically indicated.

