6.3.1 Safety assessments

The following safety assessments were performed within 28 days of randomization of the patient and subsequently at each visit during treatment phase and at End of trial treatment visit. There was no need to repeat these safety assessments at Visit 1 since screening assessments were available, unless deemed clinically required by the investigator.

Physical exam: **included an examination of major body systems and weight.**

Vital signs: **blood pressure.**

Performance status (PS) **was assessed according to ECOG scale (APPENDIX 1).**

Blood tests:

Hematology: **Hemoglobin, Absolute Neutrophils Count (ANC) and Platelets.**

Blood chemistry: **AST, ALT, Alkaline Phosphatase, Total Bilirubin and Creatinine and Creatinine clearance (at baseline only).**

During treatment phase, blood tests may be obtained up to 5 days prior to the visit.

LVEF: will be obtained during screening and every 12 weeks during treatment phase, and as required when clinically indicated. LVEF will be performed by MUGA scan or echocardiogram, using the same method at each assessment.

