### **Left Ventricular Ejection Fraction (LVEF)**

Left Ventricular Ejection Fraction (LVEF) will be collected in the eCRF to assess the percent volume of blood that is pumped by the left ventricle with each cardiac contraction to detect any cardiac toxicity associated to the drugs. LVEF will be performed by MUGA scan or echocardiogram, using the same method at each assessment.

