# **10. STATISTICAL METHODS OF ANALYSIS**

Categorical variables will be summarized in frequency tables, with the counts and percentage of subjects in each category. Percentages given in the summary tables will be rounded and thus may not always add up to exactly 100 percent. For continuous variables, summary statistics will include N, mean, standard deviation, Q1, median, Q3, minimum and maximum values (range).

SAS® version 9.1 or higher will be used for the statistical analyses.

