**BIostatistics**  
**Statistical Analysis Plan**  
**TRIO-020**  
**STAT-020-SAP**

Title	Population	Description
Afatinib Treatment Emergent Adverse Events (TEAEs)		term for each treatment group.
Serious Related Afatinib Treatment Emergent Adverse Events (TEAEs) per Grade	Safety	Summary by system organ class and preferred term for each treatment group.
Grade 3-4 Treatment Emergent Adverse Events (TEAEs)	Safety	Summary by system organ class and preferred term for each treatment group.
Grade 3-4 Treatment Emergent Adverse Events (TEAEs) per Grade	Safety	Summary by system organ class and preferred term for each treatment group.
Treatment Emergent Adverse Events (TEAEs) leading to drug discontinuation	Safety	Summary by system organ class and preferred term for each treatment group.
Treatment Emergent Adverse Events (TEAEs) leading to drug discontinuation per Grade	Safety	Summary by system organ class and preferred term for each treatment group.
Fatal Treatment Emergent Adverse Events	Safety	Summary by system organ class and preferred term for each treatment group.
ECOG Performance Status	Safety	Summary of ECOG performance status results at each time point, change from baseline at each time point. In addition, a shift table will be presented.
Blood Pressure	Safety	Summary of systolic and diastolic blood pressure results at each time point. In addition, shift tables

Title	Population	Description
		will be presented.
Weight	Safety	Summary of weight results at each time point, change from baseline at each time point.
Hematology	Safety	Summary of hematology parameters at each time point. In addition, shift tables will be presented.
Blood Chemistry	Safety	Summary of blood chemistry parameters at each time point. In addition, shift tables will be presented.
Concomitant Medications	Safety	Summary of administered concomitant medications by preferred name.

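### LVEF is summarised by visit only, with no worst post-baseline value or shift in SAP 10.6.2 and no table or listing in SAP section 11

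*SAP*

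**What the plan says.** **SAP.** Section 4.2 gives the reason for collecting LVEF: "to detect any cardiac toxicity associated to the drugs". Section 10.6.2 then plans one thing for it: "LVEF and change from baseline will be summarized by visit". In the same section, ECOG status and laboratory parameters each get a further output: "A shift table will be provided as well from baseline status to the worst status of post-baseline time points". Blood pressure gets categorised shifts from baseline, by cycle and over the study. Section 10 defines the summary of any continuous variable as N, mean, standard deviation, median, quartiles, minimum and maximum. Sections 11.1 to 11.3, which catalogue the planned tables, listings and figures, do not mention LVEF.

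**Protocol.** LVEF is measured at screening and then, per section 6.3.1, "every 12 weeks during treatment phase, and as required when clinically indicated". Table 9 in section 6.3 adds an end-of-treatment measurement. Entry requires at least 50% (section 4.1). Left ventricular systolic dysfunction of grade 3 or higher is a listed reason to stop treatment (sections 5.3.3 and 5.4.7). Section 8.4 states that "ECOG and LVEF will be summarized at baseline, along visits and at the end of trial treatment by treatment arm", and adds that toxicity shift tables will be given for these other safety data where applicable.

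**The concern.** LVEF is the only scheduled measure of cardiac function; Table 9 schedules no ECG. The question it is collected to answer concerns individual patients: who had a fall, how large it was, and how many did. A by-visit summary describes the group present at each time point. It does not follow a patient across visits, and the SAP does not say where a measurement taken between visits belongs. Those extra measurements are made because a clinician had a reason to look.

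The protocol now plans description only (synopsis, section 8), and its section 8 sets out safety summaries but no efficacy analysis. The safety outputs therefore carry much of what the final report can contribute. A gap in the only scheduled cardiac measure matters more in that setting, and it is cheap to close.

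**Working it through.** There is no figure in the plan to reproduce. The check sets the planned outputs side by side and then asks what each could reveal.

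**Step 1. Planned outputs for repeated safety measures (SAP 10.6.2, 11.1, 11.2).**

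| Measure | By-visit summary | Shift or worst value | Table in 11.1 | Listing in 11.2 |
|---|---|---|---|---|
| ECOG status | yes | baseline to worst | yes | yes |
| Blood pressure | yes | categorised, by cycle and over the study | yes | yes |
| Hematology, chemistry | yes | baseline to worst | yes | yes |
| Weight | yes | none | yes ("Summary of weight results at each time point, change from baseline at each time point") | yes |
| LVEF | yes | none | **none** | **none** |

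Weight also has no shift, but it has a table and a listing. LVEF is the only measure in 10.6.2 with neither. Section 11.3 has no LVEF figure.

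**Step 2. SAP against protocol.** Protocol 8.4 names LVEF among the data to be summarised at baseline, by visit and at end of treatment, with toxicity shift tables where applicable. SAP 10.6.2 covers the by-visit part. End of treatment is a scheduled LVEF visit in Table 9, so it can fall under that sentence, though the SAP does not say so. The SAP neither plans an LVEF shift nor says that one is not applicable.

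**Step 3. What the by-visit summary can show.** The minimum change at a scheduled visit shows the largest drop at that visit, whatever the number of patients. It does not identify the patient. It does not give a count: a near-zero first quartile is compatible with anything up to about a quarter of the patients at that visit having dropped. Minima at two visits may come from one patient or two, so the number of patients who ever dropped cannot be recovered.

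**Step 4. An off-schedule drop (assumed values, for illustration).** Baseline 60%, week 12 = 59%, unscheduled 38%, week 24 = 55%.

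- Change at scheduled visits: 59 − 60 = −1 and 55 − 60 = −5, so the largest drop shown is 5 points.
- Worst post-baseline value over all measurements: min(59, 38, 55) = 38, and 38 − 60 = −22, a drop of 22 points.

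This assumes that the unscheduled value is not assigned to a visit. The SAP does not say either way.

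**Step 5. The adverse event route.** SAP 10.6.1 tabulates adverse events by preferred term and grade and lists them by patient. The 38% value in step 4 would appear there if the investigator recorded it as an event. Protocol 7.1.2 makes recording of changes in vital signs, ECG, physical examination and laboratory results depend on judged clinical relevance, and it does not name LVEF. For laboratory data the SAP does not rely on that judgement: section 4.2 grades the values by program and 10.6.2 plans shifts.

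**The case against.** The case against has real force. A reader might infer from the by-visit sentence that only a mean change will be reported and that a single large fall would be averaged away. The documents do not support that: 10.6.2 promises both value and change, and section 10 puts the minimum beside the mean.

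A reader might also infer that a fall would go unseen altogether. That too goes beyond the text. A fall recorded as an adverse event reaches the adverse event tables and by-patient listings, and one that stops treatment also reaches the listing of events leading to drug discontinuation, with subject number, grade and action taken.

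Exclusion of unscheduled values is likewise an inference. For ECOG and laboratory data the SAP refers to scheduled time points; for LVEF it says only by visit. The handling is undefined, not defined as exclusion. Nor does the missing section 11 entry prove that LVEF will go unreported, because 10.6.2 still commits to a summary. Finally, the shift wording in Protocol 8.4 is discretionary, and 50% is an eligibility limit that the protocol does not use as a toxicity category.

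All of this stands, and it narrows the point. It does not answer three things: the missing count and identity of patients with a fall, the undefined place of measurements made on clinical indication, and the mismatch between 10.6.2 and section 11. The adverse event route covers the second only when the investigator records the fall as an event.

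**Conclusion.** The point holds in a limited form. The SAP plans no worst post-baseline LVEF and no LVEF shift, and section 11 contains no LVEF table or listing. Three comparable groups of measures in the same section get shifts, and Protocol 8.4 foresees them where applicable. The largest drop at a scheduled visit would be visible as a minimum, without the patient or the count. The loss that could go unnoticed is an off-schedule drop that was not recorded as an adverse event.

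The documents do not allow an estimate of how often that would occur. They give no number of LVEF measurements, scheduled or unscheduled, and the gap of 22 against 5 points rests on assumed values. The documents also do not support any general statement about how cardiac toxicity of this drug class would appear in LVEF data, and the conclusion does not need one. This is a worthwhile, inexpensive improvement to the safety outputs, and not evidence that LVEF will be left out of the report.

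**What to change.** Keep the by-visit summary and make these changes.

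1. **SAP 10.6.2 and 11.1:** add one LVEF table by arm on the safety population. It should hold the by-visit summary including end of treatment, the worst post-baseline value per patient over all scheduled, unscheduled and end-of-treatment measurements, its change from baseline, and a baseline-to-worst shift by CTCAE v4.0 grade. State which CTCAE term and grade limits apply, because SAP 4.2 describes programmed grading for laboratory data only. The number of patients below 50% may be added as a descriptive category, labelled as the protocol's entry limit.
2. **SAP 10.6.2:** say whether unscheduled measurements enter the by-visit summary or only the worst value.
3. **SAP 11.2:** add a by-patient LVEF listing with date, study day, value, change from baseline and method (MUGA or echocardiogram). The method column lets a reader check the protocol's rule that the same method be used throughout.

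The cost is one table and one listing, with no new assessment. SAP 4.2 states that LVEF is collected in the eCRF; that the method is a recorded field is an assumption to confirm.
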